10.3 Analysis of Primary Endpoints

Summary statistics will be estimated for all variables collected. Continuous variables will be presented as means, standard deviation, and range. Categorical variables will be summarized with frequencies and percentages. To assess the correlations between categorical clinical factors and numerical variables, t-test or ANOVA tests were conducted when data followed a normal distribution, otherwise Wilcoxon rank sum test or Kruskal-Wallis test were used instead. Pearson correlation coefficients were calculated to measure the correlation between two numerical variables, and the significance of coefficients were tested using Wald's test.

The primary endpoints are LSF and TNR for accuracy efficacy of the treatment. In the primary analyses, LSF and TNR will be estimated and compared between the two groups (MAA vs Y90) using two sample student's paired t-test. General linear model (GLM) will be further used in the multivariable analysis to estimate the adjusted efficacy of treatment (MAA vs Y90) on LSF and TNR after adjusting for other factors, respectively.

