While the assumption of MAA mirroring the Y90 microsphere biodistribution has long been suspected to be inaccurate, only recently has its impact on dosimetry been quantified, with especially compelling data sourced from the current reference standard post-Y90 PET/CT, comparing the actual Y90 absorbed dose to that estimated from the MAA[19, 25, 27]. MAA has been shown to be an inaccurate estimator of LSF and Y90 biodistribution in the liver due to several factors, including size discrepancy between MAA and Y90 microspheres, as well as free pertechnetate overestimating LSF[35-37]. MAA consistently overpredicts LSF, sometimes by greater than 100%, and has a poor linear correlation with directly measured LSF using Y90 PET (correlation coefficient: 0.682)[25]. Conversely, MAA underpredicts TNR compared to that obtained on post Y90 SPECT and PET, with a wide range of linear coefficient ranging from 0.7-0.9[8, 25]. Furthermore, retrospective direct Y90 tumor dose measurement using PET and SPECT after Y90 therapy, while resource intensive, has limited clinical benefit, since patients are rarely retreated if “inadequate” dose is delivered to tumor[8, 25]. **Hence, there is a critical need to ensure the desired dose is estimated accurately in a prospective fashion prior to administration of the therapeutic Y90.**

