These problems can be overcome by using a radioactive tracer in pre-treatment planning that is bioidentical to Y90 microspheres, which is the principle behind shunt study and treatment with Holmium-166 microspheres (¹⁶⁶Ho)[38]. Currently, ¹⁶⁶Ho is not available in the United States, and low-dose Y90 microspheres are the most readily available direct surrogate to predict LSF and tumor dose. Similar to the use of low-dose ¹⁶⁶Ho for treatment planning, a prospective personalized dosimetry method using direct yet non-toxic surrogate for therapeutic Y90 microspheres is necessary to further optimize Y90 dosimetry in a clinically pertinent manner. We believe that such efforts will not only standardize Y90 RE methodology and improve post Y90 RE outcomes under currently recommended indications but will also better allow accurate study of further indications. Additionally, LSF is a major determinant in the calculation of a safe Y90 dose as LSF > 20% is a relative contraindication to Y90 RE. Hence, it is possible that patients with inaccurately high LSF's estimated by MAA may receive lower suboptimal Y90 therapeutic doses or are entirely excluded from treatment, thus adversely impacting post-Y90 outcomes.

In summary, there is growing evidence that factoring individual patient characteristics into Y90 treatment planning are likely to significantly impact both TR and treatment tolerability. To this end, the partition model, while more resource intensive, has made great strides towards treatment individualization. However, the use of MAA in predicting post Y90 RE absorbed dose and

biodistribution is flawed and inaccurate, leading to suboptimal dose delivery, unnecessary hepatotoxicity and poor outcomes. **Therefore, we propose low-dose Y90 microspheres for therapy planning, as an alternative to MAA, to be a bioidentical therapeutic Y90 surrogate marker to better predict and thus achieve optimal therapeutic dosing.** Our long-term goal is to improve TR, PFS, and OS while reducing potential associated toxicities in patients treated with Y90 RE.

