3. OBJECTIVES AND ENDPOINTS

OBJECTIVES	ENDPOINTS
Primary	
To compare the safety and accuracy/efficacy of low dose Y90 resin microspheres and MAA in predicting the actual dose delivered to the tumor, liver, and lung after Y90 therapy.	
 • Safety: adverse events related to Y90 radioembolization and angiography will be document by physical examination, clinical laboratory test and cross-sectional imaging. • Accuracy/Efficacy: The accuracy/efficacy of MAA as a predictor of therapeutic Y90 distribution will be compared to that of low-dose Y90.
Secondary	
 1. To Identify tumor dose response thresholds (TDRT) and tumor dose distribution in patients with HCC treated with Y90 resin microspheres. 2. To optimize low dose Y90 techniques in predicting TNR and LSF. 
 • Imaging Modified Response Criteria in Solid Tumors (m-RECIST) will be used on follow-up multiphase CT or MRI at 1, 3 and 6 months post Y90 radioembolization • Tumor dose response threshold will be determined • Imaging parameters for both Y90 SPECT and PET in both low and therapeutic dose will be optimized with the goal of recommending one of either SPECT or PET as the feasible imaging modality of choice at the conclusion of the study.

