10. STATISTICAL CONSIDERATIONS

10.1 Study Design/Endpoints

Primary Objective Endpoints:

A) Accuracy/Efficacy: The accuracy/efficacy of MAA as a predictor of therapeutic Y90 distribution will be compared to that of low-dose Y90.

H₀: Y90 will have the same LSF as MAA.

H_A: Y90 will have significantly less LSF than MAA.

H₀: Y90 will have the same TNR as MAA.

H_A: Y90 will have significantly higher TNR than MAA.

B) Safety: adverse events related to Y90 radioembolization and angiography will be document by physical examination, clinical laboratory test and cross-sectional imaging.

No statistical consideration applied to the safety portion of the primary end point as it is a single arm study in which every patients undergo both mapping procedures with MAA and low-dose Y90. Detailed safety analysis plan is outlined below in section 10.5.

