10.2 Sample Size/Accrual Rate

Based on previously published data by our group, we assume mean (SD) LSF of 11.66% (10.2) for HCC using MAA[43]. Assuming LSF in low-dose Y90 is 50% lower than what is predicted by MAA and within subject correlation of 0.5 in a paired t-test, **n=30** achieves 80% power with $\alpha=0.05$. This assumption is based on several previously published studies including the work presented by our own that demonstrate that MAA overestimates true Y90 LSF by as high as 100% [25, 35-37]. Assuming mean (SD) TNR of 5.4 (2.1) using MAA is 30% lower than low-dose Y90, the power achieved with n=30 is greater than 99% [8, 25].

Emory University Hospital is one of the busiest liver transplant and cancer centers in United States. Annually, 150 HCC patients who may be transplant/surgical or palliative therapy candidates are referred to interventional radiology (IR) at Emory for liver directed therapies. Assuming a conservative accrual rate of 30%, we predict an enrollment of **n=30** patients in 6-8

months. In the event that a patient drops out either after being consented or after having a part of the study completed, a new patient will be recruited.

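### The primary objective asks which tracer better predicts delivered Y90, but the primary hypotheses, power and test compare only mean LSF and TNR between MAA and low-dose Y90, from readings the plan does not name

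*Combined protocol and SAP*

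**What the plan says.** **Objective.** Section 3 states the primary objective as "To compare the safety and accuracy/efficacy of low dose Y90 resin microspheres and MAA in predicting the actual dose delivered" to tumor, liver and lung. The Synopsis agrees, and section 10.1 opens its accuracy endpoint by treating each tracer as a predictor of the therapeutic Y90 distribution.

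**Hypotheses, power and test.** Section 10.1 then sets the LSF alternative as "Y90 will have significantly less LSF than MAA", with the mirror-image alternative (higher) for TNR. Section 10.2 powers the LSF contrast: "Assuming LSF in low-dose Y90 is 50% lower than what is predicted by MAA". Section 10.3 specifies that "LSF and TNR will be estimated and compared between the two groups (MAA vs Y90") by a paired t-test, followed by a general linear model for the same contrast.

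**Delivered dose.** Section 4.1 says that delivered dose will be compared with the dose predicted by each tracer. Section 8.1, step K, computes delivered dose from the post-therapy PET/CT. Section 10 gives this comparison no error measure, hypothesis or test. The nearest item in section 10.3 is generic: "Pearson correlation coefficients were calculated to measure the correlation between two numerical variables".

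**Readings.** In section 8.1, MAA is imaged by planar and SPECT/CT, and low-dose Y90 by planar, SPECT/CT and PET/CT. Section 7.1.2 runs dose calculations from MAA SPECT, Y90 SPECT and Y90 PET. No section says which reading supplies LSF or TNR for the primary test.

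**The concern.** Accuracy needs a reference, and the primary test has none. It asks whether one tracer gives a lower mean LSF and a higher mean TNR than the other. The link from that to accuracy is a premise in section 2.1: "MAA consistently overpredicts LSF, sometimes by greater than 100" percent, MAA underpredicts TNR, and "These problems can be overcome by using a radioactive tracer in pre-treatment planning that is bioidentical to Y90 microspheres". If the premise holds, a lower LSF and higher TNR mean a better prediction. But this is the proposition that the trial is meant to examine, and the analysis assumes it.

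The plan could therefore be followed exactly, reach significance on both endpoints, and leave the primary question open. It could endorse the less accurate tracer, or miss a tracer that is more precise without a shift in the mean. The unnamed readings add to this, because the modality alone can move LSF and TNR.

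**Working it through.** **1. The plan's own power.** Inputs from section 10.2: MAA LSF mean 11.66, SD 10.2; low-dose Y90 50% lower; within-subject correlation 0.5; n = 30; alpha 0.05. An equal SD for both tracers is an assumption.

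- Difference: 0.5 × 11.66 = 5.83
- SD of the difference: √(2 × 10.2² × (1 − 0.5)) = 10.2
- Noncentrality: 5.83 / 10.2 × √30 = 3.13, df = 29
- Power: 85.7% two-sided, 92.1% one-sided

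Section 10.2 states 80% and does not give the number of sides. The stated figure is lower than the computed one. That is a conservative discrepancy and plays no part in this point.

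**2. What the 86% depends on.** Only the MAA and low-dose Y90 readings enter the calculation. The probability is the same whatever delivered LSF turns out to be. The midpoint of the two means is (11.66 + 5.83) / 2 = 8.745. If mean delivered LSF is above about 8.75%, MAA overpredicts on average by less than 11.66 / 8.745 − 1 = 33%, and the MAA mean is the closer one. The test still favors Y90 equally often. Section 10.2 supports its effect by saying that "MAA overestimates true Y90 LSF by as high as 100" percent, which is an upper figure and does not exclude a mean below 33%.

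**3. Three scenarios, with the SD of the MAA-minus-Y90 difference near 10.2 in each.** Errors are taken as normal and independent, n = 30, two-sided 0.05. The error SDs are assumptions: 10.2 / √2 = 7.21 for each tracer in A and B. In C they are 9.8 and 2.83, and √(9.8² + 2.83²) = 10.2. The last column is a simulated paired test on absolute error in LSF points.

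| Scenario | Planned test favors Y90 | Absolute-error test favors Y90 |
|---|---|---|
| A. MAA unbiased, low-dose Y90 reads 5.83 too low | 86% | about 0% (favors MAA in 27%) |
| B. MAA reads 5.83 too high, low-dose Y90 unbiased | 86% | 27% |
| C. Both unbiased, low-dose Y90 more precise | 2.5% | nearly 100% |

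The planned test cannot tell A from B, and it does not see C.

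**4. Does anything else in section 10 measure accuracy?** The Pearson correlations are not tied to delivered dose. Even if they were, a constant offset or proportional bias leaves a correlation unchanged, so they would not measure agreement.

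**5. Does the choice of reading matter?** Phantom results in section 2.2.2, with low-dose Y90:

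| Quantity | True | Planar | SPECT | PET |
|---|---|---|---|---|
| LSF | 7.5% | 6.4% | 6.9% | 4.9% |
| TNR | 10 | not given | 6 | 10 |

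SPECT reads LSF 8% low and PET 35% low (6.9 / 7.5 and 4.9 / 7.5). SPECT reads TNR 40% low and PET is exact. The best modality differs by quantity, so the reading has to be named for each.

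**The case against.** The strongest defense is that the test matches the named endpoint: the Synopsis lists LSF and TNR as primary. That is true, but the endpoint so named does not answer the objective beside it.

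A second defense is that the design already covers delivered dose. A reader might infer from section 10 that delivered dose is ignored. The documents do not support that: section 4.1 promises the comparison, section 8.1 step K computes delivered dose, and section 2.1 calls post-therapy PET/CT the current reference standard. What is missing is the error measure, hypothesis, test and power.

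On the readings, part of the defense stands. The planar MAA limit in section 5.1 is an eligibility screen and does not conflict with planning from MAA SPECT in section 7.1.2. Section 2.1 ties the partition-model TNR to SPECT/CT, so the MAA ambiguity is mainly about LSF. The end-of-study choice between SPECT and PET in section 3 belongs to a secondary objective and does not say that the primary reading will be picked then. The gap that remains is that no low-dose reading is named, and no modality for MAA LSF.

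It is also tempting to turn the phantom errors into false-positive rates for patients. The documents do not support this: it is one phantom, it held no Tc-99m, and section 2.2.2 itself judges SPECT the better modality for LSF.

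**Conclusion.** The mismatch is real and must be fixed before analysis. The primary hypotheses, power, paired t-test and adjusted model cannot answer the stated primary objective. On the section 10.2 inputs the test favors low-dose Y90 in 86% of trials two-sided (92% one-sided), whatever Y90 was delivered, and for mean delivered LSF above 8.75% this would favor the tracer whose mean is further off. These figures rest on equal SDs, correlation 0.5 and normal differences. The three-scenario comparison also rests on assumed error SDs and is there to show behavior, not to forecast this trial.

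The unnamed readings are a second, smaller gap. The phantom shows that modality can matter, not how much it will matter in patients.

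A reader might infer a risk to participants. The documents do not support that: section 7.1.2 plans therapy from MAA SPECT, the standard of care, so what is at stake is the conclusion, not anyone's treatment.

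**What to change.** 1. In sections 3, 10.1 and 10.3, make the primary accuracy analysis a paired within-patient comparison of absolute log-ratio error against post-therapy Y90: MAA prediction versus low-dose Y90 prediction, for LSF and for TNR, with Bland-Altman limits for each tracer. Make a separate claim for each quantity, or adjust alpha (for example Holm) if success on either one counts.
2. Use the post-therapy PET/CT of section 8.1 step K as the primary reference. Before data are seen, name one MAA reading and one low-dose reading per quantity.
3. Low-dose PET and a PET reference may share a bias, so repeat the analysis with post-therapy SPECT/CT as a sensitivity analysis. It should not be a condition for the claim. If SPECT read TNR at 0.6 of truth, as in the phantom, and MAA at 0.7 (30% below low-dose Y90, section 10.2), an exact low-dose reading would look worse than MAA: |ln(1.0 / 0.6)| = 0.51 against |ln(0.7 / 0.6)| = 0.15.
4. As a further sensitivity analysis, correct the reference for residual low-dose Y90. With the 64.1-hour half-life in section 7.2.4, 15 mCi leaves 15 × 0.5^(72/64.1) = 6.9 mCi by Thursday. Against 83 mCi remaining in the vial that is 6.9 / 89.9 = 7.7% of scanned activity, and more if less than the remainder is given. The subtraction carries low-dose reading error into the reference and can count against low-dose Y90.
5. Keep the mean MAA-versus-Y90 differences as secondary, and state power for the new endpoint over a range. At n = 30, two-sided 0.05, standardized paired differences of 0.4, 0.5 and 0.6 give 56%, 75% and 89%.

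**Cost.** A changed primary endpoint, revised text and a new power statement. No extra scans or visits are needed, since the post-therapy PET/CT and SPECT/CT are already scheduled, and n stays at 30. The downside is power: the documents give no SD of prediction error, so power is uncertain and may be below 80%. In scenario B above it was only 27%.

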4. STUDY DESIGN

4.1 Overall Design

This study is a single arm phase II prospective clinical trial in which patients with HCC who are deemed suitable for Y90 radioembolization will be recruited. Patients will undergo standard of care mapping study with ^{99}Tc -MAA to plan for Y90 radioembolization therapy. The additional, non-standard of care, intervention will be to do a second mapping study using low-dose Y90 (15 mCi) before the therapeutic Y90 radioembolization.

The distribution of MAA in terms of lung shunt fraction (LSF) and tumor to normal liver activity ration (TNR) will be compared to that of low-dose Y90. The treatment planning will be performed using standard of care MAA biodistribution using partition dosimetry model.

After administration of therapeutic Y90 dose, the actual dose delivered to tumor, non-tumoral liver (NTL) and lungs will be compared to the dose predicted by MAA and low-dose Y90.

The patients will be followed-up clinically and with imaging at 1, 3 and 6 months to determine tumor response, potential treatment related toxicity and to determine TDRT.

Hypothesis: Low dose Y90 microspheres as the treatment planning radiotracer will allow more accurate prediction of therapeutic Y90 liver biodistribution, which will enable us to perform prospective personalized dosimetry for every individual patient.

The results of this study will determine the safety and efficacy of using low dose Y90 as a direct surrogate for treatment planning to ensure delivering cytotoxic Y90 dose to the targeted tumor(s), while concomitantly minimizing liver and lung toxicity with more accurate prediction of therapeutic Y90 biodistribution. **Our long-term objective is to increase the likelihood of objective tumor response, prolonged progression-free survival (PFS) and overall survival (OS) in patients with HCC treated with Y90 RE.**

The study is a single-arm in study in which each patient will undergo two sets of mapping procedure before the actual Y90 therapy. One with standard of care ^{99}Tc -MAA and one with low-dose (15 mCi) Y90 microspheres. **Therefore, the additional intervention in the study is the second mapping procedure with low-dose Y90 microspheres.** Each patient will be used as their internal control to minimize selection biases. **Additional to standard of care Y90 SPECT/CT after therapy, the patient will undergo one PET/CT after low-dose Y90 and one PET/CT after Y90 therapy.**

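### The supportive GLM in section 10.3 gives no patient effect for paired MAA and Y90 readings; fitted as written, its tracer standard error is too wide (about 1.3 to 1.4 times at the plan's correlation)

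*Combined protocol and SAP*

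**What the plan says.** The design is paired throughout. Section 4.1 states: "Each patient will be used as their internal control to minimize selection biases". Section 10.2 sizes the trial on a "within subject correlation of 0.5 in a paired t-test", and section 10.3 makes a paired t-test the primary analysis of LSF and of TNR.

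The next sentence of section 10.3 reads: "General linear model (GLM) will be further used in the multivariable analysis to estimate the adjusted efficacy of treatment (MAA vs Y90) on LSF". It extends the model to TNR and adjusts for further factors that it does not name. It mentions no patient effect, repeated-measures term or covariance structure.

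Section 10.5.4 repeats the same GLM sentence for the tumor dose response threshold and the LD 50 and LD 70 outcomes. It also plans Cox models with MAA versus Y90 as the treatment variable.

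**The concern.** Two readings from one patient are correlated, and the plan's own sample size assumes so. A linear model with tracer and patient-level covariates, but no patient term, counts 60 rows as 60 independent observations. It then uses the full between-patient spread as the error for a within-patient contrast.

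Two consequences follow. First, the interval for the tracer effect is too wide, so the report could show a significant paired t-test next to a non-significant adjusted effect for the same mean difference. The plan does not say how to read that conflict. Second, a patient-level covariate has the same value on both rows of a pair. With complete pairs and additive covariates, the adjustment therefore leaves the tracer estimate where it was.

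**Working it through.** **Inputs.** Section 10.2: "we assume mean (SD) LSF of 11.66% (10.2) for HCC using MAA"; Y90 50% lower, so the difference is 11.66 × 0.5 = 5.83 points; correlation 0.5; n = 30; alpha 0.05, with sidedness not stated. Assumed here: two-sided testing, normal data, and either equal SDs (10.2, 10.2) or a proportional Y90 SD (10.2, 5.1). The plan gives no SD for Y90.

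**The plan's own figure.** SD of the difference = 10.2 × √(2 × (1 − 0.5)) = 10.2. The paired SE is 10.2/√30 = 1.86. By the noncentral t, power at n = 30 is 85.7%, and 27 patients suffice for 80%. The stated 80% is not reproduced exactly, but it errs on the safe side. That is separate from this point.

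**Standard error.** With SDs s₁ and s₂ and correlation ρ:
- no patient term: √((s₁² + s₂²)/n)
- pairing respected: √((s₁² + s₂² − 2ρs₁s₂)/n)

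| SDs | No patient term | Paired | Ratio |
|---|---|---|---|
| 10.2, 10.2 | √(208.08/30) = 2.63 | √(104.04/30) = 1.86 | 1.41 |
| 10.2, 5.1 | √(130.05/30) = 2.08 | √(78.03/30) = 1.61 | 1.29 |

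With equal SDs the ratio reduces to 1/√(1 − ρ): 1.20 at 0.3, 1.41 at 0.5 and 1.83 at 0.7.

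**Error rate and power.** The GLM rejects when the estimate exceeds about 2.00 × its SE, but the estimate really varies with the paired SE.
- Equal SDs: the cut-off is 2.00 × 2.63 = 5.27. Power ≈ Φ((5.83 − 5.27)/1.86) = Φ(0.30) ≈ 62%. Simulation also gives 62%, against 86% for the paired test. Simulated type I error is about 0.7%, and interval coverage is about 99%.
- Y90 SD halved: simulated power is about 84% against 94% paired, with type I error about 1.3%.

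A figure of 59% comes from the two-sample formula. It applies only if the readings really were independent, so 62% is the right one for paired data with the pairing ignored.

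**Conflicting results.** With equal SDs, a non-significant GLM appears beside a significant paired test in about 24% of simulated trials (86 − 62). With the halved SD, the gap in power is about 10 points (94 − 84).

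**Effect of covariates.** With equal SDs, suppose covariates explain 30% or 60% of the between-patient variance (assumed). The SE is then still 1.29 or 1.17 times too wide, and power is 70% or 78%.

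**Does adjustment move the estimate?** In one simulated set of 30 complete pairs the tracer effect was −5.127 unadjusted, with a patient-level covariate, and with patient as a factor. The SEs were 2.23, 2.24 and 1.54; the last equals the paired t-test SE. A tracer-by-covariate interaction, with the covariate not centred, moved the coefficient to −5.09. With 5 of the 30 Y90 readings removed, the estimates were −5.10 unadjusted, −5.15 adjusted and −6.35 with patient as a factor.

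**The case against.** The strongest reply is that the plan is silent rather than wrong. A reader might infer that it declares the two readings independent, but no section says so. A general linear model can carry patient as a factor or a repeated-measures structure, and the authors clearly know the data are paired. That stands: this is a model left open, not a stated error. It does not settle the matter, because the text describes the tracers as two groups, and section 10.5.4 goes on to Cox models by tracer although each patient receives both. An analyst who fitted 60 independent rows would comply fully with the plan.

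A second reply is that the model is supportive. The paired t-test carries the primary conclusion, and the error is conservative, so it cannot manufacture a benefit for low-dose Y90. That also stands, and it limits the severity.

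A reader might also infer that adjustment can never change the tracer effect. That holds only with complete pairs and additive patient-level covariates. Section 7.6 lets a patient who discontinues low-dose mapping remain on study, so incomplete pairs are possible. Interactions, or covariates that differ by tracer such as imaging modality, can move the estimate too.

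Finally, section 2.1 cites a "correlation coefficient: 0.682", which would give a ratio of 1/√(1 − 0.682) = 1.77 with equal SDs. That figure relates MAA to LSF measured directly by Y90 PET, not to a low-dose Y90 mapping reading, so 1.77 is illustrative only.

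**Conclusion.** The point holds as an underspecified supportive model that, fitted in its plainest form, gives the wrong standard error. At correlation 0.5 the tracer SE is 1.41 times too wide with equal SDs and 1.29 times with the Y90 SD halved. Type I error is about 0.7% or 1.3% instead of 5%. Power is about 62% or 84%, against 86% or 94% paired. These sizes rest on the plan's LSF mean, SD, effect and correlation, on two-sided testing and normal data, and on the assumed Y90 SD; covariates that explain between-patient variance reduce them.

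A reader might conclude that the primary result is compromised. The documents do not support that: the primary test is paired, the trial was sized on it, and neither its estimate nor its p-value depends on the GLM. The practical harm is an over-wide supportive interval and a contradictory pair of results. This should be fixed before analysis.

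**What to change.** Replace the GLM sentence in section 10.3 with one of these:

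- a linear mixed model with a random patient intercept, a tracer effect, and covariates entered as tracer-by-covariate interactions; or
- a regression of the within-patient difference on baseline covariates centred at their means, where the intercept is the tracer effect.

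Name the covariates in advance and keep them few at n = 30; centre them in either model. With complete pairs and no covariates, the difference regression is the paired t-test, so the supportive and primary analyses can no longer disagree merely because the pairing was dropped. The slopes show which patients have a larger difference between MAA and low-dose Y90. They do not measure MAA error against delivered dose, for which the plan's reference is the post-therapy PET/CT calculation (section 8.1, step K).

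Make the matching change in section 10.5.4 wherever an outcome is measured under both tracers.

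The cost is one sentence in section 10.3 and its counterpart in section 10.5.4. The data and the software stay the same.
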